### 5.2 Data Conventions

In the context of this SAP, 5 periods will be considered:

**Screening period:** from the date of signing informed consent to:

- For participants who enter the IVDP: the day prior to the first IVIg administration with 23:59 added
- For participants who enter directly the IVMP: the day prior to the first IVIg administration during IVMP with 23:59 added or if the participant discontinued during the screening period the date of study termination with 23:59 added as time part
- For participants who discontinued during the screening period: the date of study termination with 23:59 added as time part

**IVIg Dependency period (IVDP):** Only defined for participants with uncertain dependency to IVIg during screening: from the first IVIg administration date with 00:00 added as part time during IVDP to the day prior to the first IVIg administration with 23:59 added in IMVP or if the participant discontinued during the IVDP period the date of study termination with 23:59 added as time part

**IVIg Monitoring period (IVMP):** from the first IVIg administration date with 00:00 added as time part during IVMP to prior to the first IMP administration (time/date) -1 minute or if the participant discontinued during the IVMP period the date of study termination with 23:59 added as time part

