## 6.2.7 Missing, Unused, and Spurious Data

### 6.2.7.1 Adverse events missing dates

AEs will be considered treatment-emergent based on their start date/time.

Imputation of missing/partial AE dates/time will be performed only to identify treatment-emergent AEs. If the AE start date/time is incomplete or missing, the AE will be considered treatment-emergent unless the available part of the AE start or stop date/time provide evidence that the event did not occur following initiation of IMP. The following rules allow for an imputed start and stop date that adheres to this convention:

For partial or missing AE start date/time the following imputation will be applied:

1. If year is not missing and is after the year of first IMP dose:
  - a. If month is missing, then month will be imputed as January.
  - b. If day is missing, then day will be imputed as the first of the month.
2. If year is not missing and is the same as the year of the first IMP dose:
  - a. If month is missing, then impute the month as the month of the first dose date.
  - b. If day is missing, and the month is the same as the month of the first dose date, then impute day as the day of the first dose date.
  - c. If day is missing but month is after the month of first dose date, then impute day as the first day of the month.
3. If year is missing then impute the date of the first IMP administration.
4. If the start date is completely missing, but the AE is either ongoing or the stop date or imputed stop date (in case of partially missing stop date) is after the first dose date then impute the start date as the first dose date.
5. For any cases involving the rules above, if the AE stop date or imputed stop date (in case of partially missing stop date) is before the AE start date, then do not impute the AE start date and assume that the AE is treatment-emergent for the purpose of the analysis. Further, if the AE stop date or imputed AE stop date (in case of partially missing stop date) occurs prior to the first dose date, do not impute the AE start date, and assume that the AE is not treatment-emergent.

For partial or missing AE start time the following imputation will be applied:

1. If date or imputed date is the date of the of the first IMP dose, then the time will be the time of the IMP administration
2. If date or imputed date is different from the date of the of the first IMP dose, then time will be 00 h 00 min.

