**Table 10 Adverse Event Definitions**

	Definition
Treatment-emergent adverse event (TEAE)	Treatment-emergent AEs are defined as AEs with onset on or after the first administration of IMP
Treatment Related AE	Any AE reported by the investigator as treatment related (ie, “Relationship to ARGX-117/Placebo= Related” in the CRF “Adverse event” page) and those of missing relationship.
IVIg Related AE	Any AE reported by the investigator as IVIg related (ie, “Relationship to IVIg treatment= Related” in the CRF “Adverse event” page) and those of missing relationship.
Procedure Related AE	Any AE reported by the investigator as procedure related (ie, “Relationship to any study procedure = Related”) and those of /missing relationship.
Serious Adverse Events (SAEs)	Any AE with “Is this a serious adverse event?” = Yes in the CRF “Adverse event” page.
Non serious Adverse Events	Any AE with “Is this a serious adverse event?” = No in the CRF “Adverse event” page.
Adverse Events Leading to Interruption of IMP	Any AE with “ARGX-117/Placebo interrupted?” = Yes in the CRF “Adverse event” page.
Adverse Events Leading to Permanent Treatment Discontinuation	Any AE with “ARGX-117/Placebo withdrawn” = Yes in the CRF “Adverse event” page.
Adverse Events Leading to Death	Any AE with fatal outcome or AE with NCI CTCAE grade = 5
Adverse Event of Special Interest	AESIs are defined as events with grade ≥ 3 and a PT that falls under the MedDRA SOC Infections and infestations.
Adverse Event of Hypersensitivity Reactions	Any AE with PT from SMQ (narrow) selection for hypersensitivity reaction
Adverse events of Anaphylactic Reaction	Any AE with PT from SMQ (narrow) selection for anaphylactic reaction
Adverse Events of Local Reactions	Any AE with MedDRA PT in the MedDRA High Level Group Term of administration site reactions, regardless of time of onset.

Summary tables of TEAEs will be presented for the DBTP (SAF set).

AE will also be allocated to the first period that is possible based on the available part of the AE start and stop date/time. If, for a participant not entering the safety follow-up period or LTE, an AE occurs following V14 or treatment discontinuation, then the AE will be counted in the DBTP.

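### An adverse event (AE) with an incomplete start date can be treatment-emergent under SAP 6.2.7.1 yet, read literally, belong to a pre-treatment period under 6.4.1

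*SAP*

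**What the plan says.** Four parts of the SAP bear on this.

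- **Treatment-emergent flag (6.2.7.1).** The default is conservative: "If the AE start date/time is incomplete or missing, the AE will be considered treatment-emergent unless" the known part of the start or stop date shows that the event did not follow the start of IMP. For a month-only date the rule begins "If day is missing, and the month is the same as the month of the first dose date, then impute day as the day", meaning that on which IMP was first given. For a missing time it begins "If date or imputed date is the date of the of the first IMP dose, then the time will be the time", meaning when that IMP was given. A year-only date in the first-dose year, or a missing start for an event that is ongoing or stopped after first dose, also goes to the first-dose date. The scope is limited: "Imputation of missing/partial AE dates/time will be performed only to identify treatment-emergent AEs".
- **Period allocation (6.4.1, text below Table 10).** "AE will also be allocated to the first period that is possible based on the available part of the AE start and stop date/time". The next sentence covers participants who enter neither follow-up nor the LTE, and counts their late events in the DBTP.
- **Periods (5.2).** "In the context of this SAP, 5 periods will be considered". Screening, IVDP and IVMP come before treatment. The IVMP runs "from the first IVIg administration date with 00:00 added as time part during IVMP to prior to the first IMP administration (time/date) -1 minute". For AEs, both the DBTP and the combined DBTP and safety follow-up period start at first IMP.
- **Tables (6.4.1 and Table 24).** AE summaries are either for the DBTP or for the DBTP plus safety follow-up.

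**The concern.** Two rules act on the same event and point in opposite directions. The flag rule resolves doubt towards treatment. The allocation rule, applied to the known part of the date alone, resolves the same doubt towards the earliest period, and three of the five periods precede treatment. The limit on imputation in 6.2.7.1 means the imputed start cannot be carried over to bring the two into line.

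AEs are a primary endpoint (section 3.1). If the summary tables select on the allocated period, an event that the plan has declared treatment-emergent would not appear in them. The listings of treatment-emergent SAEs, AESIs and withdrawals carry no period restriction, so a serious event could stand in Listing 16.2.6.7.2 and be absent from Table 14.3.1.7.

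**Working it through.** The SAP gives no figure here, so there is nothing to reproduce. The check traces the rules and then tests how general the result is.

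**One case.** Take a first dose on 15 March and an AE recorded as starting in March, still ongoing.

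1. Under 6.2.7.1 the day is set to 15 March and the time to the time of dosing. The AE is treatment-emergent.
2. Under 6.4.1 the known part is March. A start on 1 to 14 March is possible, and those days lie before first IMP.
3. Under 5.2 they fall in the IVMP, which ends one minute before first IMP. The earliest possible period is the IVMP.

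**All first-dose dates.** Section 2.1 gives nominal IVMP lengths of 35, 49, 63 and 77 days. A calendar month has at most 31 days, so the first day of the first-dose month always lies inside the IVMP. Every date in 2022 and 2023 was taken as a possible first-dose date (2 × 365 = 730), with an assumed dose time of 10:00 and a month-only AE start in the same month:

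| IVMP length | Treatment-emergent (6.2.7.1) | Earliest period IVMP | Earliest period before IVMP | Earliest period DBTP |
|---|---|---|---|---|
| 35, 49, 63 or 77 days | 730 | 730 | 0 | 0 |
| 29 days (assumption: shortened by visit windows) | 730 | 716 | 14 | 0 |

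The 14 are first doses on the 31st of a month (7 such months × 2 years). A first dose on the 1st of a month is no exception, because the time from 00:00 to dosing on that day still belongs to the IVMP.

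**Other incomplete dates.** The same conflict arises where a pre-dose start is possible:

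- dated on the first-dose day without a time: treatment-emergent by time imputation, earliest period IVMP;
- year only, in the first-dose year: treatment-emergent, earliest period possibly as far back as screening;
- no start date, ongoing: treatment-emergent, earliest period screening.

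An event known to have stopped before first dose is not affected, since 6.2.7.1 makes it not treatment-emergent.

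**Scale.** A cohort of 24 randomized 2:1 has 24 × 2/3 = 16 active and 24 × 1/3 = 8 placebo participants. One participant missing from a table row changes the incidence by 1/16 = 6.25 or 1/8 = 12.5 percentage points. That applies only if the event is the participant's sole event in that row.

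**The case against.** The strongest reply is that the allocation sentence was meant only to separate the DBTP from follow-up for events already known to be treatment-emergent. It says that AEs are also allocated, so it adds to the flag rather than replacing it. It follows directly on the statement that TEAE tables are for the DBTP, and the next sentence deals with late events. The opening of 6.4.1 likewise sets only the upper end of the DBTP. A TEAE by definition starts on or after first IMP, so placing it in the IVMP is incoherent. On this reading, taking the earliest period moves doubtful events into the DBTP, which is conservative.

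This reading is plausible, but the text does not state it. The sentence speaks of AEs, not TEAEs, although Table 10 just above defines the latter. Nothing limits the period to those from first IMP onward, and nothing gives the flag precedence. A programmer who follows the words would allocate these events to the IVMP or earlier.

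Three stronger inferences do not stand:

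- A reader might infer that these events are tabulated in a pre-treatment period. No AE table for screening, IVDP or IVMP is planned.
- A reader might infer that the events vanish from the report. All AEs, including pre-treatment ones, are listed.
- A reader might infer that the affected events cluster around first-infusion reactions. Nothing in the SAP supports this. Infusions take place at scheduled visits with at least 1 hour of monitoring afterwards, where a missing day or month is least likely.

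**Conclusion.** The two rules conflict as written. An AE dated only to the first-dose month, and not known to have stopped before dosing, is treatment-emergent and has a pre-treatment earliest possible period in every case checked. The same holds for the other incomplete dates above when a pre-dose start is possible.

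That such events are left out of the primary safety summaries is conditional, although a reader might take it as certain. It depends on the tables selecting on the allocated period. The table titles, and the statement in 6.4.1 that event rates are derived for the periods of 5.2, point that way, but the SAP never says so expressly. The number of incomplete dates is not given and may be small, so the 6.25 and 12.5 points show the weight of one participant and do not estimate an effect.

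This is a conflict of wording that touches a primary endpoint and should be resolved. It is not a demonstrated loss of events.

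**What to change.** Replace the allocation sentence in 6.4.1 with wording to this effect: an AE that is treatment-emergent under 6.2.7.1 is allocated to the earliest possible period on or after the first IMP administration; only AEs that are not treatment-emergent are allocated to a pre-treatment period.

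With this change all 730 cases in the check fall in the DBTP, which begins at the first IMP date and time. The cost is one sentence in the SAP and one condition in the AE dataset program. If the narrower meaning was intended all along, no result changes and the sentence simply records it.

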### Overview Tables of TEAE

Overview summary tables will be presented by treatment group for the DBTP. The number and percentage of participants who had at least 1 TEAE and the event rate per 100 PYFU in each of the following categories will be displayed during the DBTP in the SAF set:

- Treatment-emergent adverse event (TEAE)
- IMP Related TEAE
- IVIg Related TEAE
- Procedure Related TEAE
- treatment-emergent SAE
- Serious IMP related TEAE
- TEAEs for which IMP was interrupted
- TEAE Leading to Withdrawal of IMP
- TEAE leading to Death
- TEAE with CTCAE grade  $\geq 3$
- treatment-emergent AESI
- TEAE of hypersensitivity reactions
- TEAE of anaphylactic reactions
- TEAE of local reactions

Additionally, an overview table of TEAEs will be displayed during the DBTP and SAFFU periods combined in the SAF set.

In these tabulations, each participant will contribute only once (ie, via the most related occurrence or the most intense occurrence) to each of the incidence rates in the descriptive analysis, regardless of the number of episodes that occurred.

### Summary Tables of AE by SOC and PT

Summary tables will be presented by treatment group. The selected TEAEs listed above, excluding fatal events and those leading to interruption of IMP, will also be summarized in terms of participant incidence rates and number of events by SOC and PT during the DBTP in the SAF set.

A summary table of TEAE by SOC and PT will be provided for during the DBTP and SAFFU periods combined in the SAF set. Note that in any tabulation, a participant will contribute only once to the count for a given adverse event (SOC or Preferred Term), regardless of the number of episodes that occurred.

All AEs will be listed, including pretreatment AEs.

The following by-participant listings will be presented in the SAF set:

- all adverse events
- treatment-emergent SAE
- TEAE leading to withdrawal of IMP
- TEAE Leading to Interruption of IMP
- treatment-emergent AESI
- TEAE leading to death

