### Safety Follow-up Period

After completing the 16-week DBTP, participants may enroll in an LTE study (which is not part of ARGX-117-2002) and continue to receive ARGX-117; otherwise, participants will enter the safety follow-up (SFU) period (without ARGX-117 treatment). The safety follow-up period will characterize safety, PK, and PD during the elimination of ARGX-117. The SFU period will begin after the DBTP and will continue for at least 15 months; the day of the first SFU visit will be considered the start of the SFU period.

A schematic of the study design is shown in [Figure 2](#). The schedule of activities is in appendix 9.1, further details are available in the study protocol.

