**Double Blind Treatment Period (DBTP):**

- For the efficacy endpoints: From the first IMP administration date/time to V14 with 23:59 added as time part or date of early treatment discontinuation visit with 23:59 added as time part
- For AE and concomitant medication: From the first IMP administration date/time to:
  - Informed consent of LTE for participants who do enter into LTE. Date of informed consent corresponds to the treatment completion date in the main study. All data on the eCRF will be considered to belong to this period
  - 23h59 the day prior to the 1st FU visit at week 4 for those participants who do not enter into LTE or date of early study discontinuation with 23:59 added as time part if participant discontinued the study before FUV1
  - Date of study discontinuation with 23:59 added for participants who early discontinued study and do not enter in the safety follow up period

**DBTP and Safety Follow-up period:** For AE, from the first IMP administration date/time to:

- Informed consent of LTE for participants who do enter into LTE. Date of informed consent corresponds to the treatment completion/discontinuation date. All data on the eCRF will be considered to belong to this period
- Study discontinuation for those participants who do not enter into LTE

Participants who entered into LTE are participants who were eligible for LTE and signed the informed consent form.

**Study Day 1 IDVP:** The day of the first IVIg administration during IDVP

**Study Day 1 IVMP:** The day of the first IVIg administration during IVMP

**Study Day 1:** The day of the first administration of ARGX-117 or placebo

**Study Day 1 FU:** The day following V14/ED visit (D113) (for participants who do not enter into the LTE)

**End of Treatment Visit:** The V14 visit (D113) for participants who completed DBTP, or the visit following IMP discontinuation for participants who discontinue IMP prior to V14 (D113) or the last IMP administration date for participants who are on-going in the DBTP at the data cut-off date .

**End of Study Visit:** The V14 visit (D113) for participants entering the LTE, or the last recorded date in the DBTP or SFU period for participants not entering the LTE.

Scheduled or Unscheduled visits which do not fall into the visit windows will be listed, but not included in tables or graphs.

- **Conversion factors:**
  - 1 month = 30.4375 days
  - 1 year = 365.25 days
  - 1 week = 7 days
  - °C = (°F - 32)/1.8
- **Additional rules**

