Descriptive statistics for immunogenicity titer values will include the number of observed values, arithmetic mean, SE, 95% CI, median, Q1, Q3, minimum, maximum, the GM, and geometric CV%.

Mean, 95% CI, Q1, Q3, and median will be presented with one more decimal place than the measured values. SE and SD will be presented with 2 more decimal places than the measured values. Minimum and maximum will be presented with the same number of decimal places as the measured values.

For event-type safety data, the number and percentage of participants with an event will be shown. The denominator will be all participants in the analysis set per treatment arm.

For cross-tabulations, the denominator will be the number of participants in the analysis set per treatment arm. For tables where results are shown by analysis visit, the denominator will be the number of participants in the analysis set per treatment arm and analysis visit. Missing values will not be included in the denominator count when computing percentages. Percentages will be presented with 1 decimal place.

If a participant is re-screened, only data from the last screening will be displayed.

Data from the SFU period will be listed only.

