Table	14.2.4.13	Overall Treatment-Emergent Adverse Events of Hypersensitivity by Overall Antidrug Antibodies Participant Classification - <Treatment group> -Safety Set		x	x
Table	14.2.4.14	Overall Treatment-Emergent Adverse Events of Anaphylactic Reaction by Overall Antidrug Antibodies Participant Classification - <Treatment group> -Safety Set		x	x
Table	14.2.4.15	Overall Treatment-Emergent Adverse Events of Local Reaction by Overall Antidrug Antibodies Participant Classification - <Treatment group> -Safety Set		x	x

CRS-BS-TP-000005 V 2.0

ADVERSE EVENTS					
Table	14.3.1.1	Overview of Treatment-Emergent Adverse Events during DBTP - Safety Set	x	x	x
Table	14.3.1.2	Overview of Treatment Emergent Adverse Events from start of DBTP up to the end of Safety Follow-up period - Safety Set		x	x
Table	14.3.1.3	Treatment Emergent Adverse Events by SOC and PT during DBTP - Safety Set	x	x	x
Table	14.3.1.4	Treatment Emergent Adverse Events Related to IMP by SOC and PT during DBTP - Safety Set		x	x
Table	14.3.1.5	Treatment Emergent Adverse Events Related to IVIg by SOC and PT during DBTP -Safety Set		x	x
Table	14.3.1.6	Treatment Emergent Adverse Events Related to Procedure by SOC and PT during DBTP - Safety Set		x	x
Table	14.3.1.7	Serious Treatment Emergent Adverse Events by SOC and PT during DBTP - Safety Set		x	x
Table	14.3.1.8	Serious Treatment Emergent Adverse Events Related to IMP by SOC and PT during DBTP - Safety Set		x	x
Table	14.3.1.9	Non Serious Treatment Emergent Adverse Events by SOC and PT during DBTP - Safety Set		x	x
Table	14.3.1.10	Treatment Emergent Adverse Events Leading to Withdrawal of IMP by SOC and PT during DBTP - Safety Set		x	x
Table	14.3.1.11	CTCAE Grade 3 or Higher Treatment Emergent Adverse Events by SOC and PT during DBTP -Safety set		x	x

Table	14.3.1.12	Treatment Emergent Adverse Events of Special Interest by SOC and PT during DBTP - Safety Set		x	x
Table	14.3.1.13	Treatment Emergent Adverse Events by Worst CTCAE Grade SOC and PT during DBTP - Safety Set		x	x
Table	14.3.1.14	Treatment Emergent Adverse Events of Hypersensitivity Reaction during DBTP - Safety Set		x	x
Table	14.3.1.15	Treatment Emergent Adverse Events of Anaphylactic Reaction during DBTP - Safety Set		x	x
Table	14.3.1.16	Treatment Emergent Adverse Events of Local Reaction during DBTP - Safety Set		x	x
Table	14.3.1.17	Treatment Emergent Adverse Events by SOC and PT from start of DBTP up to the end of Safety Follow-up Period - Safety Set		x	x
LABORATORY					

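### The two adverse-event tables over DBTP plus safety follow-up use windows of about 16 or up to about 80 weeks depending on LTE entry, and the SOC/PT table names no person-time rate

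*SAP*

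**What the plan says.** - **Window (SAP 5.2).** The combined period runs "For AE, from the first IMP administration date/time to" one of two ends. For one group it is "Informed consent of LTE for participants who do enter into LTE", a date the SAP equates with treatment completion or discontinuation. For the other it is "Study discontinuation for those participants who do not enter into LTE".
- **Length of the SFU (2.1, Table 20).** "The SFU period will begin after the DBTP and will continue for at least 15 months". The last scheduled visit is FUV6 at week 64. Under 5.4, participants who stop IMP early are also followed in the SFU.
- **Tables (6.4.1, Table 24).** Two tables span the combined period, both for interim analysis 2 and the final analysis. One is the overview, 14.3.1.2. The other is announced in 6.4.1 as "A summary table of TEAE by SOC and PT will be provided for during the DBTP and SAFFU periods combined in the SAF set" and appears in the output list as 14.3.1.17, titled "Treatment Emergent Adverse Events by SOC and PT from start of DBTP up to the end of Safety Follow-up Period - Safety Set".
- **Denominator (6.2.1).** For event-type safety data: "The denominator will be all participants in the analysis set per treatment arm".
- **Statistic (6.4.1).** The SOC/PT tables are described as participant incidence and number of events. A rate per 100 patient-years of follow-up (PYFU) is derived for both the DBTP and the combined period, but its display is specified only for the overview.
- **TEAE definition (Table 10).** Any onset on or after first IMP, with no upper limit after the last dose.
- **General rule (6.2.1).** SFU data are to be listed and nothing more, which does not fit the two combined tables.

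**The concern.** Who gets the short or the long window is settled after randomisation, by stopping IMP early or by not rolling over to the LTE. Either may depend on tolerability or response, and so on treatment. In Table 14.3.1.17 a participant who enters the LTE stays in the denominator but cannot contribute an event after about week 16. A participant who completes the SFU can contribute for some 64 weeks more. If the arms differ in the share entering the SFU, their percentages and event counts differ even when the event hazard is identical.

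At stake is how two supplementary safety tables, shown by treatment group, will be read. Nothing in the SAP warns the reader that follow-up differs within and between the columns.

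**Working it through.** The SAP gives no event rate, SFU-entry rate or power figure on this point, so there is no planned figure to reproduce beyond the arm sizes: 24 at 2:1 is 16 + 8 per cohort, and two cohorts with pooled placebo give 16 + 16 + 16 = 48.

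**1. Window lengths.** LTE entrant: D113 is (113 − 1)/7 = 16 weeks. SFU completer: 16 + 64 = 80 weeks. The text's 15 months is 15 × 30.4375/7 = 65.2 weeks, consistent with week 64. The ratio is 80/16 = 5. At a constant rate, 64/80 = 80% of an SFU completer's expected events fall after an LTE entrant's window has closed.

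**2. Crude percentage with no drug effect.** Let *s* be the share of an arm that completes the SFU and λ a constant hazard of first event per year, equal in both arms. Both are assumptions.

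I(t) = 1 − exp(−λt/52.18); crude % = (1 − s)·I(16) + s·I(80); mean follow-up = 16 + 64s weeks.

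- λ = 1 (plausible for any TEAE): I(16) = 26.4%, I(80) = 78.4%.
- λ = 0.1 (an uncommon term): I(16) = 3.0%, I(80) = 14.2%.

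| SFU completers, active v placebo (one cohort) | Mean follow-up, weeks | λ = 1 | λ = 0.1 |
|---|---|---|---|
| 1/16 v 2/8 | 20 v 32 | 29.7% v 39.4% | 3.7% v 5.8% |
| 3/16 v 0/8 | 28 v 16 | 36.2% v 26.4% | 5.1% v 3.0% |

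The false difference is about 10 points at λ = 1 and about 2 points at λ = 0.1. Its sign follows whichever arm has more SFU completers. For scale, one participant is 100/16 = 6.25 points on active and 100/8 = 12.5 points in one cohort's placebo group.

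**3. Two arms of 16 (pooled placebo).** With shares of 0 v 12.5% (0 v 2 of 16) and 16-week incidences of 5, 10, 20 and 30%, the false differences are 2.2, 3.9, 5.9 and 6.6 points. With equal shares the difference is 0.

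**4. Would shares be unequal by chance?** With the same non-entry probability in both arms, exact binomial enumeration over 16 and 8 participants gives a probability of 0.667 (5% non-entry) or 0.807 (10%) that mean follow-up differs by at least 10%. At 5% and 10% these equal the probability that the shares differ at all. They show only that small arms rarely match exactly, and say nothing about size.

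**5. Does the PYFU rate repair it?** With a constant hazard, yes. For a 16-week incidence of 20% the rate is −ln(0.8)/16 × 52.18 × 100 = 72.8 per 100 PY at any *s*. If the hazard halves after treatment, the rate is 72.8 × (16 + 0.5·64s)/(16 + 64s), which is 62.4 at s = 10% and 52.9 at s = 30%. The rate reduces the problem but still mixes on-treatment and post-treatment time.

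**The case against.** The strongest reply is that the safety comparison is already on the right window. Of the 17 adverse-event tables in Table 24, 15 cover the DBTP only (14.3.1.1 and 14.3.1.3 to 14.3.1.16), including serious, related, grade 3 or higher and special-interest events. That stands. A reader might infer that the primary safety objective is compromised. The documents do not support this, because the long follow-up enters only two supplementary tables. (Under 5.2 the DBTP window for adverse events also runs on for non-entrants, but only to the day before the week-4 follow-up visit.)

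Other points that stand:
- The distortion needs unequal SFU entry. The SAP gives no split by arm, and its modification history gives the small number entering the SFU as the reason for dropping PK parameters.
- Eighty weeks is a maximum. Early stoppers have a shorter DBTP, those who leave the study are followed for less, and at interim analysis 2 some participants are still ongoing.
- The SFU is meant to observe safety while drug is being eliminated, so a cumulative table has a purpose and early SFU events are not simply off-drug.
- The trial is exploratory with no formal testing, and adverse events are also listed by participant.

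It can also be said that 6.4.1 derives a PYFU rate for the combined period, and that its sentence on the combined SOC/PT table names no statistic at all. That is fair: the crude percentages are inferred from the general description of SOC/PT tables and the denominator rule. But nothing places the rate in Table 14.3.1.17, so a programmer following the text would produce counts and percentages only.

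**Conclusion.** The point holds in a limited form. As written, Table 14.3.1.17, and the percentages beside the rate in 14.3.1.2, compare arms over windows of about 16 or up to about 80 weeks, fixed by events after randomisation, with every treated participant in the denominator. If SFU entry differs between arms, a difference appears without a drug effect: about 2 points for an uncommon term and about 10 points for any TEAE in the scenarios above. These figures rest on assumed hazards (0.1 and 1 per year), assumed SFU shares, equal and constant hazards, and full SFU completion.

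A reader might infer that one arm will show more harm. The SAP does not support a direction or an actual size. With few SFU entrants the effect on most individual terms is likely below one participant. Severity is low: these are descriptive, supplementary tables.

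**What to change.** In SAP 6.4.1:

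1. Report TEAEs with onset in the SFU in a separate table by arm, with participants who entered the SFU as denominator and their person-years shown. Start it where 5.2 closes the DBTP window for adverse events, so that no event is counted twice or lost.
2. If Table 14.3.1.17 is kept, add person-years per arm and events per 100 PYFU for each SOC and PT. Add a footnote that the percentages are not comparable between arms because follow-up depends on LTE entry, and that the rate mixes on-treatment and post-treatment time.
3. Reconcile the rule in 6.2.1 that SFU data are only listed with the combined tables in 6.4.1 and the output list.

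The DBTP tables stay as they are. The cost is SAP wording, one new table shell and extra columns in another, from dates and rates already derived. The drawback is small denominators in the SFU table.
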